The Official Title

A Randomized Controlled Study of Lenvatinib Following Liver Transplantation in
Patients with High-Risk Hepatocellular Carcinoma

NCT number: none

Date of the document: November 16, 2019

Hepatocellular carcinoma (HCC) is the third leading cause of cancer deaths worldwide and accounts for about 13,000 deaths in the United States per year [1]. Liver transplantation offers selected patients with localized HCC a chance for cure. For those meeting the Milan criteria, defined as a single tumor 2–5 cm or three or fewer nodules, each 3 cm or less, and no gross vascular invasion, 5 year survival for transplanted patients is about 75% [2, 3]. Meeting these criteria provides additional priority for transplantation in the US. However, for those with HCC beyond the Milan criteria, whether determined pre-transplant or by pathologic evaluation of the explant, the risk of recurrence may be as high as 70% at 2 years after transplantation [4]. There are few studies evaluating adjuvant therapy after resection or transplantation for HCC, and there is no standard of care for the treatment of these patients. Finding an effective agent which decreases recurrence rates in high-risk patients would be a significant advance.

1. Research Purpose

The aim of this study is to observe the efficacy and safety of lenvatinib in preventing high-risk recurrence of hepatocellular carcinoma patients after liver transplantation.

2. Research Protocol

The research is an open, randomized, single-center study. Patients with high-risk recurrence of hepatocellular carcinoma who underwent liver transplantation are included according to the criteria of admission. After operation, the regimen of calcineurin inhibitors, mycophenolate mofetil, sirolimus or everolimus with glucocorticoids removed at an early stage are used. Patients enrolled in the study were randomly allocated in the lenvatinib group (54 patients) and the control group (54 patients) after stable condition. Patients in the control group are given supportive treatment and regular follow-up. Patients in the lenvatinib group are given lenvatinib within 1-2 months after operation (dose: body weight < 60 kg: 8 mg/day, body weight \geq 60 kg 12 mg/day). The baseline data of patients are collected before allocation. Serum and imaging examination are checked regularly every month to monitor the

recurrence of hepatocellular carcinoma and the side effects of lenvatinib. The efficacy and safety of lenvatinib in patients of high-risk hepatocellular carcinoma are observed, and the clinicopathological factors affecting the efficacy of lenvatinib are analyzed.

When side effects of lenvatinib occur, the dosage can be reduced according to the patients' condition until discontinuation. When tumor recurrence occurs, a multidisciplinary team will draw up specific treatment plans according to the patients'

condition, including surgical resection, interventional therapy, radiofrequency therapy, radiotherapy and targeted therapy (Patients in the control group can add lenvatinib, and patients in the lenvatinib group can decide whether to continue using it according to the patients' condition).

3. Research population

3.1 This study is a single center clinical study. The cases are from patients with hepatocellular carcinoma who underwent liver transplantation in the liver surgery department of Shanghai Renji Hospital.

3.2 Inclusion criteria

- Patients at high risk of recurrence of hepatocellular carcinoma after liver transplantation: extended Milan criteria, without vascular invasion (except for microvascular invasion suggested by pathology after operation)
- Male or female patients aged 18 to 75.
- ECOG physical condition was 0-2 points.
- Child-Pugh A grade of liver function.
- Targeted therapy is acceptable within 1-2 months after liver transplantation. Immunosuppressive regimen consists of calcineurin inhibitor, mycophenolate mofetil and sirolimus.
- No history of surgical resection of liver tumors and targeted drug therapy before liver transplantation.
- Good liver, kidney and bone marrow function: serum albumin > 28g/L, total bilirubin \leq 3 mg/dL (51.3 μ mol/l), ALT and AST \leq 5 times the upper limit of

normal range; serum creatinine \leq 1.5 times the upper limit of normal range; hemoglobin $>$ 90 g/L, neutrophil count (ANC) $>$ 1.5×10^9 /L, platelet count $>$ 60×10^9 /L; PT-INR $<$ 2.3, or PT within 6 seconds over normal upper limit.

- For fertile female patients, the serum/urine pregnancy test should be negative within 7 days before treatment.
- All male and female participants must take reliable contraceptive measures during the trial and within four weeks after the end of the trial.
- The participants have the capability of oral medication.
- The participants must sign the consent form.

3.3 Exclusion criteria

- Life expectancy is less than 3 months
- The recurrence and metastasis of hepatocellular carcinoma are highly suspected.
- Patients are with other malignant tumors simultaneously. λ Patients are anaphylaxis to the inactive ingredients of lenvatinib or drugs.
- Pregnant or lactating women (Female participants need pregnancy test within 7 days before treatment).
- Preoperative history of severe cardiovascular disease: congestive heart failure $>$ NYHA grade 2; active coronary heart disease (myocardial infarction occurred within 6 months before entry into the study); severe arrhythmia requiring antiarrhythmic treatment (allowable use of beta-blockers or digoxin); uncontrolled hypertension.
- History of HIV infection.
- Severe clinical active infections ($>$ NCI-CTCAE version 3.0).
- Epilepsy patients requires medication (e.g. steroids or antiepileptic drugs).
- Patients with kidney diseases requires renal dialysis.
- Drug abuse, medical symptoms, mental illness or social status that may interfere with participants' participation in research or evaluation of research results.
- Patients who could not swallow oral drugs, such as those with severe upper gastrointestinal obstruction and need gastric tube feeding.
- Other anti-angiogenesis therapies, surgery, TACE, local therapy and systemic

chemotherapy were given before the treatment after liver transplantation.

3.4 Exit research

- Participants who have one of the following conditions must stop using drugs immediately and exit the study. At the same time, a comprehensive evaluation will be conducted within 1-2 weeks of the last medication (adverse events, recurrence of tumors, medication for treatment):
- Patients are with poor compliance.
- Prohibited drugs or other drugs that are likely to produce toxicity or result in deviation are used.
- Concurrent diseases or situations that may significantly affect the clinical status and the end point of the study have occurred.
- Clinical signs and laboratory examinations confirm the diagnosis of pregnancy.
- Another malignant tumor has developed.
- The participants are lost to follow-up.
- The participants died.
- Participants or their legal representatives demanded withdrawal from the study

4. Research Progress

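### Section 3.4 ties stopping drug to leaving the study and is not reconciled with the 5-year follow-up in section 4.4, so outcomes after exit may go uncollected

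*Combined protocol and SAP*

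**What the plan says.** Section 3.4 sets one rule for eight conditions: "Participants who have one of the following conditions must stop using drugs immediately and exit the study". For those patients "a comprehensive evaluation will be conducted within 1-2 weeks of the last medication", covering adverse events, recurrence and medication.

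Three of the eight (loss to follow-up, death, withdrawal from the study) end observation anyway. The other five are:
- poor compliance
- taking a prohibited drug, or another drug that might cause toxicity or a deviation
- a concurrent condition, in these words: "Concurrent diseases or situations that may significantly affect the clinical status and the end point of the study have occurred"
- confirmed pregnancy
- a second cancer: "Another malignant tumor has developed"

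Section 4.4 sets monthly blood tests and ultrasound, 3-monthly MR or CT of the liver and CT of the lung, and 5 years of follow-up. The primary endpoint is time to recurrence. Overall survival counts death from any cause, and both recurrence-free and overall survival are to be given at 1, 3 and 5 years. The section does not mention patients who left under section 3.4.

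Section 6.1 allows a 10% loss and connects it, in loose wording, with what is probably the intention-to-treat population. Section 6.2 gives no analysis population, censoring rule or handling of exits.

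Section 2 describes an open trial in which "Patients in the control group are given supportive treatment and regular follow-up". On toxicity it says: "When side effects of lenvatinib occur, the dosage can be reduced according to the patients' condition until discontinuation". That is dose reduction or stopping, and section 3.4 does not list it as an exit.

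**The concern.** Stopping a drug and stopping observation are separate events, and section 3.4 merges them. If the rule is followed literally, a patient who complies poorly or develops a second cancer has one more evaluation and is then censored. Recurrences and deaths after that point are not collected, and no analysis can restore them.

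The log-rank test and Kaplan-Meier estimates assume that censoring is unrelated to outcome. Three features put that in doubt:
- One trigger is a condition that may affect the end point itself.
- Poor compliance and a possible effect on the end point are undefined judgements, made by people who know the allocation.
- Controls take no study drug, so compliance exits could fall mainly on the lenvatinib arm. The timing from the last medication has no clear meaning for a control.

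Informative exits that are unequal between arms would bias the test and the hazard ratio. If they are equal, the comparison under no effect is about unbiased, but the planned 1-, 3- and 5-year rates are still distorted. For overall survival, patients with serious concurrent disease or a second malignancy are the ones whose later deaths would be missed.

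**Working it through.** **1. The plan's own figure.** Inputs from section 6.1: medians 12 and 24 months (HR 0.5 with exponential times), 1:1 allocation, 12 months of recruitment, 36 months in total, 10% loss. Two-sided alpha 0.05 and 80% power are assumptions, because the plan gives p < 0.05 without sidedness and gives no power.
- Events (Schoenfeld): 4 × (1.960 + 0.842)² / (ln 0.5)² = 65.4, so 66.
- Event probability with uniform accrual: 1 − [exp(−λ·24) − exp(−λ·36)] / (12λ), where λ = ln 2 / median. Control: 1 − (0.250 − 0.125)/0.693 = 0.820. Lenvatinib: 1 − (0.500 − 0.354)/0.347 = 0.577. Mean 0.699.
- Per group: 66 / 0.699 / 2 = 47.2, against 47 stated. Then 47 / 0.90 = 52.2, so 53, as stated. Section 2 says 54.

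**2. Exits unrelated to prognosis, equal in both arms.** Power = Φ(0.693 × √events / 2 − 1.96). With 53 per arm, the 36-month cutoff and an assumed share exiting by 24 months:

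| Exits | Events | Power |
|---|---|---|
| 0% | 74.0 | 84.7% |
| 10% | 70.4 | 82.8% |
| 20% | 66.6 | 80.7% |
| 30% | 62.7 | 78.4% |

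Simulation with 54 per arm and all exits in the first 12 months gives 85, 82, 80 and 76% for the same shares. With 5 years per patient it gives 92, 90, 88 and 84%.

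**3. Exits related to prognosis, no true effect.** Simulated, with every exit rate and risk ratio assumed:
- 54 per arm, median 12 months in both arms, 36-month cutoff.
- 30% of patients have 2 or 3 times the recurrence hazard of the rest.
- Exit times are uniform over 0-12 months. Recurrences up to exit count, and deaths are not modelled.
- In the strong model all exits come from the high-hazard 30%. In the mild model 60% of them do.
- False benefit means log-rank Z < −1.96, nominally 2.5%. With 40,000 trials per scenario the Monte Carlo standard error is about 0.1 points, and runs without exits gave 2.5-2.6%.

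| Exits, lenvatinib vs control | Who exits | HR | False benefit |
|---|---|---|---|
| 10% vs 5% | higher risk, mild | 0.99 | 2.7-2.9% |
| 10% vs 5% | higher risk, strong | 0.98 | 3.2-3.3% |
| 20% vs 5% | higher risk, mild | 0.98-0.97 | 3.0-3.3% |
| 20% vs 5% | higher risk, strong | 0.96-0.94 | 4.0-4.6% |
| 20% vs 20% | higher risk, strong | 1.00 | 2.5-2.6% |
| 20% vs 0% | lower risk only (3 times hazard) | 1.04 | 1.6-1.8% |

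The last row comes from smaller runs of 6,000 and 8,000 trials. At 30% vs 5% the strong model gives HR 0.92-0.90 and 5.5-7.0%. There 0.30/0.30 = 100% of high-hazard lenvatinib patients exit and nobody else does, so this is an extreme case. At 20% the share is 0.20/0.30, or two-thirds.

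**4. Equal 20% informative exits at the planned medians, 5 years per patient.** When exiting patients are at higher risk, the Kaplan-Meier recurrence-free rates come out too high. In the mild model the excess is 0.3-2.0 points across arms and time points. In the strong model it is at most 4.7 points (lenvatinib at 3 years, 3 times hazard: 0.371 without exits, 0.418 with them).

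**The case against.** The strongest reply is that section 3.4 is a loosely worded list of dispositions, not a rule for ending data collection. Taken literally it tells the dead and the lost to stop drug and attend an evaluation. Section 4.4 states 5 years of follow-up with no exception, and section 6.1 seems to have an intention-to-treat population in mind. This stands in part: the wording is loose, and the sponsor may intend to follow everyone. But poor compliance and another malignancy share one exit phrase with loss, death and withdrawal, and nothing in sections 2 to 6 gives it a different meaning for them. A site would have to guess.

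The reply also holds on several points of size. Nothing in the documents links compliance, prohibited drugs, pregnancy or a second malignancy to the hazard of recurrence. The concurrent-condition trigger says only that the condition may have an effect. Small imbalances do almost nothing, and uninformative exits are largely covered by the sample size.

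A reader might infer three stronger claims that the documents do not support:
- **Patients who stop lenvatinib for toxicity leave the study.** Section 2 provides for reduction and discontinuation, and section 3.4 does not list toxicity.
- **The rule favours lenvatinib.** If lower-risk patients exit from the lenvatinib arm alone, the HR moves above 1. No control exits are needed for that.
- **The trial is underpowered because of exits.** The calculation in step 2 does not show this at exits up to about 20%.

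**Conclusion.** The point holds as an unreconciled rule that should be fixed. As written, section 3.4 ends outcome collection for patients who could still be followed, and section 4.4 does not bring them back. The bias could go in either direction and its size is unknown, because the documents give no exit rates.

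Under the assumed rates it ranges from negligible (10% versus 5%, HR 0.98-0.99) to modest. At 20% versus 5% with higher-risk patients exiting, HR is 0.98-0.94 and false benefit 3.0-4.6% against a nominal 2.5%. At 20% versus 0% with lower-risk patients exiting, HR is about 1.04. The larger strong-model figures should not be read as forecasts.

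Uninformative exits up to about 20% leave power near the assumed 80% with 53-54 per group, provided nothing else is lost. Effects on overall survival were not computed. Confidence is medium, because the sponsor may already intend to follow everyone.

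**What to change.** Leave the drug-stopping criteria in section 3.4 as they are, and reconcile sections 3.4 and 4.4 on follow-up:
- State that stopping drug does not end outcome follow-up. Recurrence and survival status continue to be collected for all randomised patients in both arms unless consent to follow-up is withdrawn.
- Leave the type of examination for pregnant participants to the investigators, so that the imaging schedule in section 4.4 is not imposed on them without exception.
- Say how section 3.4 applies to control patients, including what its evaluation is timed from when there is no study drug.
- State that all randomised patients are analysed in their allocated arm.
- Keep the 10% in section 6.1 for true loss to follow-up only.
- Report exits by arm and reason.

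The cost is a few sentences in sections 3.4, 4.4 and 6.1, and modest extra follow-up on the existing schedule. Counting outcomes after patients stop drug may also give a less favourable hazard ratio.

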4.1 Participants

- Participants must sign the consent form.
- Participants are confirmed in compliance with inclusion and exclusion criteria.
- Basic data including height, weight and blood pressure are collected.
- Clinical blood test including liver and kidney function, complete blood count, coagulation function, blood glucose and lipid index are collected.
- Serological and imaging examinations are collected before treatment.

4.2 Allocation

Participants are randomly allocated to lenvatinib group and control group through software.

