6.1 Sample size

Logrank test is used to analyze the survival rates. The median recurrence time after liver transplantation for HCC which extends the Milan criteria is 12 months according to the literature. The median recurrence time is expected to increase to 24 months after treatment with lenvatinib. The experimental group and the control group were enrolled in the group according to the ratio of 1:1. The recruiting time is expected to be 12 months and the study time is expected to be 36 months. At least 47 cases were calculated for each group. Since it is assumed that 10% of the samples may be lost due to the adjustment of the intentional treatment population, 53 cases will be needed for each group eventually.

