6.2 Statistical Methods

The researcher is responsible for checking and preserving all the data, and handing over the data results to professional statisticians for analysis. Survival curves are estimated using the Kaplan – Meier method. For identification of independent prognostic factors, the Cox proportional hazard model was used in the univariate and multivariate analyses. All statistical analyses were performed using the SPSS (version 22.0). Statistical significance was defined as $p < 0.05$.

7. Emergency Event Management

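### Neither the allocation nor the only stated treatment comparison uses microvascular invasion, although both levels are admitted; a stratified log-rank test would protect power if it is prognostic (worth considering)

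*Combined protocol and SAP*

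**What the plan says.** Section 2 places allocation after transplantation: "Patients enrolled in the study were randomly allocated in the lenvatinib group (54 patients) and the control group (54 patients) after stable condition". Section 4.2 is a single sentence: "Participants are randomly allocated to lenvatinib group and control group through software". It names no stratification factor, blocking or minimisation.

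The only test named for comparing the groups is in section 6.1: "Logrank test is used to analyze the survival rates". No strata or covariates are attached to it. Section 6.2 gives the Cox model a different job: "For identification of independent prognostic factors, the Cox proportional hazard model was used in the univariate and multivariate analyses". No covariates are listed, and the model is not linked to the treatment comparison. Section 2 also plans to study which clinical and pathological features affect how well lenvatinib works, which is again not the primary comparison.

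Section 3.2 admits tumours "without vascular invasion (except for microvascular invasion suggested by pathology after operation". Patients with and without microvascular invasion are therefore both eligible.

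On baseline data, section 2 states "The baseline data of patients are collected before allocation" and section 4.1 states "Serological and imaging examinations are collected before treatment". The section 4.1 list does not include explant pathology. It names no tumour marker and does not date the serology relative to transplantation. Alpha-fetoprotein, its variants and abnormal prothrombin are named only for monthly follow-up, in section 4.4.

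**The concern.** Section 3.2 singles out microvascular invasion as the one form of vascular invasion that does not exclude a patient. The plan thus distinguishes this feature at entry and then does not use it in allocation or in the primary comparison.

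If the feature is prognostic, two things follow. First, a plain log-rank test on a mixed population has less power than a test stratified by the feature, even when the arms are balanced. Second, with about 54 patients per arm, a chance difference in the share of high-risk patients is quite possible, and it would make the observed result harder to interpret. The sample size has limited slack for this: 47 per group gives about 80% power only if no strong prognostic factor is being ignored.

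**Working it through.** **Inputs from the plan (sections 2, 6.1, 6.2).** Control median 12 months; lenvatinib median 24 months (hazard ratio 0.5 under exponential times); 1:1 allocation; 12 months of recruitment; 36 months in total; 10% loss; significance at p < 0.05. Section 6.1 plans 53 per group; section 2 states 54.

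**Assumed, because the documents do not say.** Two-sided test; 80% power (it reproduces the stated 47); microvascular invasion present in 30-50% of patients; marker hazard ratio for recurrence 1 to 4; treatment hazard ratio 0.5 within each marker level.

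**Step 1: reproduce the plan's own figure.**
- Events = 4(1.960 + 0.842)² / (ln 0.5)² = 65.3.
- Probability of an event with uniform recruitment = 1 − [e^(−24λ) − e^(−36λ)] / (12λ).
- Control, λ = ln 2/12: 1 − (0.250 − 0.125)/0.693 = 0.820.
- Lenvatinib, λ = ln 2/24: 1 − (0.500 − 0.354)/0.347 = 0.577.
- Mean 0.699, so n per group = 65.3/(2 × 0.699), about 46.8, rounded up to 47.
- 47/0.9 = 52.2, rounded up to 53.

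Both stated numbers reproduce. Power by the same formula is 80.2% at 47 per group and 84.7% at 53.

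**Step 2: power of the plain and the stratified test.** Trials were simulated with a binary marker of prevalence p and hazard ratio H. The low-risk control hazard λ₀ solves (1 − p)e^(−12λ₀) + p·e^(−12Hλ₀) = 0.5, so the control median stays at 12 months. Allocation is unstratified 1:1. The plain statistic is U/√V. The stratified one is (U₀ + U₁)/√(V₀ + V₁), with U and V computed within each marker level. Ranges cover prevalence 30% and 50%.

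| Marker hazard ratio | 53 per arm: plain | 53 per arm: stratified | 47 per arm: plain | 47 per arm: stratified |
|---|---|---|---|---|
| 1.5 | 83-84% | 84% | 78% | 78-79% |
| 2 | 79-80% | 82-83% | 74-75% | 77-78% |
| 2.5 | 76-78% | 83% | not run | not run |
| 3 | 73-74% | 81-83% | 66-68% | 77% |
| 4 | not run | not run | 59-61% | 75-76% |

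With 3,000 runs, simulation error is about ±1.5 points (1.96 × √(0.75 × 0.25/3000) = 0.015). At hazard ratio 3 and 50% prevalence, other simulation runs put the plain test at about 71%. If the marker has no effect, stratifying costs about 1 point at 53 per arm and up to 2 at 47.

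**Step 3: validity.** With no treatment effect, the plain test rejected in 4.4-5.9% of simulated trials (47 per arm, 4,000 runs per setting). Type I error is not inflated.

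**Step 4: where the gain comes from.** Stratifying the allocation while keeping the plain test raised power by only about 0-2 points. Nearly all of the gain comes from the analysis.

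**Step 5: chance imbalance.** With 54 of 108 patients per arm (hypergeometric), the chance of a difference of at least 10 percentage points is 29%, 24% and 34% at prevalence 30%, 40% and 50%. Ten points is about six patients (0.10 × 54 = 5.4). A difference of at least 20 points has a chance of 2-5%.

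**The case against.** Unstratified randomisation followed by a log-rank test is a valid and common design. Imbalance under randomisation is chance, not bias, and the usual 10-point threshold amounts to about six patients. The documents never say that microvascular invasion predicts recurrence, let alone how strongly. Up to a marker hazard ratio of 2, the plain test at 53 per arm stays near 80%. The plan also foresees multivariable Cox models. All of this stands, except that those Cox models are not tied to the treatment comparison and so do not protect it. It is also true that if 0.5 is the overall hazard ratio rather than the ratio within marker levels, the plain test keeps about 80% power. Adjustment would then add power above that level rather than restore a loss.

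A reader might infer several stronger points that the documents do not support:

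- **That baseline serology is drawn only after the tumour has been removed.** Enrolment after transplantation, and the exclusion of patients in whom "The recurrence and metastasis of hepatocellular carcinoma are highly suspected", make this plausible. Section 4.1 does not date the sample, however, and does not rule out pre-transplant records. The 1-2 months in section 2 is when lenvatinib starts, not when blood is drawn.
- **That the trial is biased or its type I error inflated.** Step 3 shows otherwise.
- **That section 4.2 is where power is lost.** Stratified allocation alone changes little.
- **That pre-transplant alpha-fetoprotein must be a covariate.** Its effect was not evaluated here.
- **That the change is free.** It needs no extra patients, but it does need recorded data. The documents do not say when explant reports become available.

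**Conclusion.** The point holds as an efficiency improvement to consider. The plan admits both levels of microvascular invasion and uses the feature neither in allocation nor in its only stated treatment comparison. The resulting test is valid. How much power it gives up depends on an assumed marker strength: negligible at a hazard ratio of 1.5, about 2-4 points at 2, about 5-7 points at 2.5 and about 7-11 points at 3 (53 per arm, prevalence 30-50%, treatment hazard ratio 0.5 within marker levels, exponential times). The cost if the marker is not prognostic is about 1 point, or up to 2 at 47 per arm. That asymmetry favours the change, but the missing evidence on marker strength keeps it from being a requirement.

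**What to change.** - **Sections 6.1 and 6.2 (most of the benefit).** Prespecify the primary test as a log-rank test stratified by microvascular invasion (present or absent). Give the treatment hazard ratio from a Cox model that includes microvascular invasion. Keep the search for prognostic factors as a separate analysis.
- **Section 4.1.** Add microvascular invasion on the explant as a baseline item. State whether the baseline serology is pre- or post-transplant. Recording pre-transplant alpha-fetoprotein and adding it as a covariate is optional.
- **Section 4.2.** If the explant report is available by the time of allocation, stratify the software allocation on microvascular invasion using permuted blocks. If it is not, the stratified analysis can still be done, because the explant predates allocation.

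Cost: one or two extra recorded items, a setting in the allocation software where feasible, a change of wording in section 6, and about 1-2 points of power at most if the marker turns out not to be prognostic. No extra patients are needed. The choice should be fixed before outcome data are seen.
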